16.1.6. MISSING DATA METHODS FOR SECONDARY EFFICACY VARIABLES

16.1.6.1. DRC-adjudicated and Investigator-assessed overall response, clinical response, radiological response, mycological response

- Patients with a missing overall response at a specific visit will be considered as failures at the visit.

Document:	\\weedc-vnasc01\BIOSdata\F2G\F901318\		
Author:		Version Number:	3.0
		Version Date:	06Apr2023
Template No.:	CS_TP_BS016 Revision 6	Reference:	CS_WI_BS005
Effective Date:	02Dec2019		

F2G Ltd.
PROTOCOL F901318/0032

- Patients with a missing clinical response at a specific visit will be considered as failures at the visit.
- In cases where the radiological test was not done, or results are not available, or the test is not applicable/relevant, this information will appear as such in outputs. In cases where the radiological response is missing (and not captured in one of the before mentioned options), it will be indicated as “Missing” in tables.
- Patients with a missing mycological response at a specific visit will be assessed according to criteria in [Table D](#) as either presumed eradication (success), presumed persistence or no mycological follow-up results available (failure) at the visit.

Note: All mITT patients will be counted in the denominator of the %/ rate calculation at every visit through Day 84, even if they discontinue early. For mycological response, all patients with mycological evidence at baseline will be counted in the denominator of the %/rate calculation.

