
Concomitant Antifungal Therapy:
	
In order to meaningfully analyse the efficacy of F901318, it is important to avoid concomitant use of other systemic antifungal agents with known or potential activity against the primary fungal infection. The constraints on the choice of additional agents may be complex and thus use of any other systemic concomitant antifungal or combination treatment (such as addition of terbinafine for confirmed Lomentospora prolificans infections or an echinocandin to manage infection due to Candida) is permitted but is discouraged.
 
Antifungal combinations should be based on the Investigator’s clinical judgement and must be discussed with the MM.
 
Depending on the treatment given, an extra visit for Unscheduled Trough PK sampling (for rapid PK analysis of F901318) may be required 3 to 5 days after starting or stopping such concomitant medication, to support evaluation of potential DDIs.

Criteria for Evaluation:
 
Efficacy Endpoints:
 
Primary Endpoint:
 
 • DRC-adjudicated overall response rate by pathogen at Day 42. 
Secondary Endpoints (all by pathogen and also in aggregate)
 
 • DRC-adjudicated overall response at Day 7, Day 14, Day 28, main study phase EOT, Day 84 and 4-week FU. • Clinical response at Day 7, Day 14, Day 28, Day 42, main study phase EOT, Day 84 and 4-week FU. • Where appropriate for the IFD, radiological response at Day 7, Day 14, Day 28, Day 42, main study phase EOT, Day 84 and 4-week FU. • Mycological response by pathogen and by susceptibility category at Day 7, Day 14, Day 28, Day 42, main study phase EOT, Day 84 and 4-week FU. • Investigator-assessed overall response (integration of clinical, radiological, and mycological response) at Day 7, Day 14, Day 28, Day 42, main study phase EOT, Day 84 and 4-week FU. • All-cause mortality at Day 42, main study phase EOT, Day 84 and 4-week FU. • Quality of life (patient-reported outcome) [REDACTED], based on the EQ-5D-5L questionnaire. 
Note: For patients who will receive ET beyond Day 90, the Day 84 visit and the main study phase EOT visit will be combined into a single Day 84/EOS/EOT visit on approximately Day 90. Subsequent visits [REDACTED] to assess the safety of continued treatment and to assess the need for further treatment, and there will be a FU visit 4 weeks after ET is completed.
 
Safety:
	

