≥ 25% to < 50% improvement in aggregate (across all lesions if more than one lesion)
No change 0%* to < 25 % improvement in aggregate (across all lesions if more than one lesion)
Worsening in aggregate (across all lesions if more than one lesion)
No signs on radiological images at screening
Results not available (i.e. visit and/or radiological assessment was not performed at the scheduled timepoint (Day 7, Day 14, Day 28, Day 42, EOT, Day 84 or 4-week FU)).

Radiological response will also be presented grouped in categories and presented at output level:

Document: \\weedc-vnasc01\BIOSdata\F2G\F901318\ [Redacted]
Author: [Redacted] Version Number: 3.0
Version Date: 06Apr2023
Template No.: CS_TP_BS016 Revision 6 Reference: CS_WI_BS005
Effective Date: 02Dec2019

F2G Ltd.
PROTOCOL F901318/0032

- “Success” if response is $\geq 90\%$ improvement in aggregate (across all lesions if more than one lesion)
- “Improvement” if response is ≥ 50 to $< 90\%$ improvement in aggregate (across all lesions if more than one lesion) and $\geq 25\%$ to $< 50\%$ improvement in aggregate (across all lesions if more than one lesion)
- “Stable” if response is No change 0%* to $< 25\%$ improvement in aggregate (across all lesions if more than one lesion)
- “Worsening” if response is Worsening* in aggregate (across all lesions if more than one lesion)
- “Death” if death
- “Not Evaluable/Missing” if response is (No signs on radiological images at screening, Results not available, Missing)

16.1.5.5. DRC-adjudicated and Investigator-assessed mycological response at Day 7, Day 14, Day 28, Day 42, main study phase EOT, Day 84, and 4-week follow-up

DRC-adjudicated and Investigator-assessed mycological response at Day 7, Day 14, Day 28, Day 42, main study phase EOT, Day 84, and 4-week follow-up are also secondary efficacy variables.

DRC-adjudicated mycological response is determined by an independent DRC and collected in a separate DRC adjudicated outcome database.

Investigator-assessed mycological response is collected on the Investigator’s diagnostic and response assessment eCRF page.

Table D presents the criteria for mycological response.

Table D: Criteria for mycological response

Mycological Response	Criteria
Eradication	Eradication of the original causative organism cultured or identified by histology/cytology at baseline and no emergence of new causative organisms at that visit.

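### Grouped radiological percentages use an all-mITT denominator that includes patients with no radiological signs at screening, and pool those patients with missing imaging

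*SAP*

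**What the plan says.** SAP 16.1.6.1 covers missing data for four responses: overall, clinical, radiological and mycological. Its closing note states: "All mITT patients will be counted in the denominator of the %/ rate calculation at every visit through Day 84". The next sentence makes one exception: "For mycological response, all patients with mycological evidence at baseline will be counted in the denominator of the %/rate calculation". Radiology has no equivalent sentence.

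SAP 16.1.5.4 lists the radiological categories in Table C, where having no signs at screening is a category of its own. It then adds a second display: "Radiological response will also be presented grouped in categories and presented at output level". In that display *Success* means at least 90% improvement, and *Improvement* covers 25% to under 90%. The last group, *Not Evaluable/Missing*, collects three Table C outcomes: "No signs on radiological images at screening, Results not available, Missing".

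For radiology that was not done, gave no available result, or was not relevant, 16.1.6.1 says: "or the test is not applicable/relevant, this information will appear as such in outputs". It says nothing about removing those patients from the denominator.

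The protocol synopsis words the endpoint as "Where appropriate for the IFD, radiological response at Day 7, Day 14, Day 28" and later visits. SAP 16.1.7.3 plans descriptive summaries and listings only.

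**The concern.** A patient whose screening images show no sign of the infection has nothing that can shrink. That patient can stay clear or develop a new lesion, but cannot enter *Success* or *Improvement* at any visit. Keeping such patients in the denominator lowers both percentages by an amount that reflects case mix and says nothing about the drug. The SAP recognises this problem for mycology and solves it there by requiring baseline evidence. Radiology has the same structure and gets no such rule.

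The pooling adds a second difficulty. Having no lesion at screening and having a lesion that was never re-imaged are different facts, and Protocol 6.3.1.2 records them as different categories. Once they share a row in the grouped table, a reader cannot tell how much imaging was actually missed or recover the restricted denominator from that table. Grouped percentages are the ones most likely to be quoted from a secondary endpoint.

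**Working it through.** The documents state no radiological response rate and no share of patients without signs at screening, so there is no figure of the plan to reproduce. The check applies the written rules and then does the arithmetic.

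**Inputs**
- Denominator: all N patients in the mITT set, at visits through Day 84 (SAP 16.1.6.1).
- Exception for baseline evidence: mycology only (SAP 16.1.6.1).
- Grouped categories and the pooled row: SAP 16.1.5.4.
- N = 200 for illustration, assuming the mITT set equals the planned enrolment of approximately 200 (SAP 3.1). The percentages do not depend on N.
- q, the share of mITT with no signs at screening: not in the documents; assumed 5%, 10%, 20%, 30%.
- p, the rate in a given improvement group among patients with baseline signs: not in the documents; assumed 20%, 40%, 50%.

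**Step 1: who can be in the numerator.** Let x be the number of patients in *Success* (or *Improvement*) at a visit. All of them had signs at screening, and N(1 − q) patients had signs, so p = x / [N(1 − q)].

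**Step 2: what the grouped table reports.** Reported % = x / N = p × (1 − q). The shortfall is p − p(1 − q) = p × q. The largest attainable value is 1 − q, which is 95% at q = 5% and 70% at q = 30%.

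**Step 3: numbers.** Reported % (shortfall in percentage points):

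| q | p = 20% | p = 40% | p = 50% |
|---|---|---|---|
| 5% | 19.0 (1.0) | 38.0 (2.0) | 47.5 (2.5) |
| 10% | 18.0 (2.0) | 36.0 (4.0) | 45.0 (5.0) |
| 20% | 16.0 (4.0) | 32.0 (8.0) | 40.0 (10.0) |
| 30% | 14.0 (6.0) | 28.0 (12.0) | 35.0 (15.0) |

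As counts, for q = 20% and p = 40%: 200 × 0.80 = 160 patients with signs, and 160 × 0.40 = 64 in the group. The table would show 64/200 = 32.0%; the restricted figure is 64/160 = 40.0%.

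**Step 4: the pooled row.** Suppose nobody died and every patient with baseline signs was re-imaged. *Not Evaluable/Missing* would still read q, that is 5% to 30% over the assumed range, although no follow-up image of a baseline lesion was missing.

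**Step 5: what the rule does not reach.**
- Table C, ungrouped, keeps the no-signs patients in their own row, so the restricted denominator can be rebuilt from it.
- The footnote to Table A in SAP 16.1.1 requires only clinical and mycological data for overall success, so this denominator rule does not enter the Day 42 primary endpoint.
- The denominator note stops at Day 84 and leaves the 4-week follow-up unstated.

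**The case against.** The strongest reply is that no radiological response rate is planned. SAP 16.1.7.2 and 16.1.7.4 give clinical and mycological response a success proportion with a Clopper-Pearson interval; 16.1.7.3 gives radiology only descriptive summaries and listings. *Success* is then one row of a category distribution, and no failure is imputed to anyone. The grouped table is additional to Table C, which keeps the information, and the text promises that non-applicable results will be shown as such. The table shells supplied with the SAP are not available here, and Appendix 1 asks for denominators to be identified. All of this stands and limits the consequence. It does not remove the point: followed as written, the note divides by all mITT patients and the grouped row merges the two kinds of patient.

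Three stronger readings are tempting, and the documents do not support them.

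- *The SAP departs from the protocol endpoint.* A reader might take the protocol's qualifier about appropriateness to mean a lesion visible at screening. It can equally mean that imaging is relevant to the type or site of infection, so a departure is not shown.
- *Comparison across the five disease categories is distorted.* Protocol Appendix 2 gives some reason to expect q to differ: probable lower respiratory tract aspergillosis needs an imaging feature, while proven disease does not need clinical features. One proven route does, however, require an abnormal site, clinically or radiologically, and no q is given for any category. It is a possibility, not a demonstrated effect.
- *The understatement has a known size.* It does not; q is assumed throughout. Deaths and absent follow-up images also lower the *Success* row, and they properly remain in it.

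Keeping every mITT patient does have one merit: a new lesion in a patient without baseline signs has a denominator. The remedy has to deal with that case explicitly.

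**Conclusion.** The point holds as a defect in how a descriptive secondary endpoint is tabulated. For any q above zero, the grouped *Success* and *Improvement* percentages fall below the rate among patients with baseline signs, by p × q. The direction follows from the SAP's own rules. The size, about 1 to 15 percentage points, rests on assumed q of 5–30% and assumed rates of 20–50%, none of which the documents give. The grouped *Not Evaluable/Missing* row overstates missing imaging for the same reason.

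A reader should not infer from this that the trial's main result is understated, or that the information is lost. The rule does not reach the Day 42 DRC-adjudicated response, and Table C preserves the no-signs count. The change is still worth making, because it extends to radiology a rule the SAP already applies to mycology.

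**What to change.** 1. In SAP 16.1.6.1, after the mycology sentence, state that percentages for radiological response use mITT patients with radiological signs of the infection at screening. Patients in that group who lack a later image stay in the denominator. State the denominator for the 4-week follow-up in the same way, within the patients the SAP already considers at that visit.
2. In SAP 16.1.5.4, take the no-signs-at-screening patients out of *Not Evaluable/Missing* and show them as a separate *Not applicable* count outside that denominator.
3. Report new lesions in these patients as a separate count. They should not be added to *Worsening* within the restricted denominator, because they would then enter it only after a bad outcome and inflate that row.

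The cost is a few sentences in the SAP and one table shell; the category is already collected on the response assessment. The downside is a smaller denominator for a descriptive secondary table.

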16.1.6.2. All-cause mortality rate

If at a visit a patient is reported as having died, then the patient is considered as a death for subsequent visits.

For cases where a death was not reported at a previous visit, and survival status is missing/not done at the specific visit, the survival status will be indicated as “Missing”.

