Based on the DRC-adjudicated and Investigator-assessed mycological response categorized as Success/Failure, a response rate will be calculated based on all patients included in the mITT population with a baseline culture result available. Patients with a mycology evaluation of “No mycological Follow-up results available” will be assigned an outcome of presumed eradication if they are deemed a clinical success and a presumed failure if they are deemed a clinical failure, or clinical response is missing. Mycological success will include patients classified as a success or a presumed eradication. In addition a 95% CI for a single binomial proportion will be calculated.

All-cause mortality at Day 42, main study phase EOT, Day 84 and 4-week FU*

Mortality rates will be derived at Day 42, main study phase EOT, Day 84 and 4-week FU* based on all patients in the mITT population. In addition a 95% CI for a single binomial proportion will be calculated. Also, Kaplan-Meier analyses will be performed at Day 42, main study phase EOT, Day 84 and 4-week FU*, summarising median time to death (stratified by DRC-adjudicated disease category). A reported death will be carried forward for all future visits. A patient without reported death for the specific visit analysed (Day 42, main study phase EOT, Day 84 or 4-week FU*) will be censored for the specific visit analysed.

**Note: For patients planning to receive ET beyond Day 90, the Day 84 visit and the main study phase EOT visit will be combined into a single Day 84/EOS/EOT visit on approximately Day 90 and there will be no 4-week FU visit in the main study phase. As judged relevant, subanalyses will be performed to account for this difference in observation periods.*

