16.1.2. MISSING DATA METHODS FOR PRIMARY EFFICACY VARIABLE

Patients with a missing DRC-adjudicated overall response at Day 42 will be considered as failures.

Note: All mITT patients will be counted in the denominator of the %/ rate calculation at every visit through Day 84,

Document:	\\weedc-vnasc01\BIOSdata\F2G\F901318\		
Author:		Version Number:	3.0
		Version Date:	06Apr2023
Template No.:	CS_TP_BS016 Revision 6	Reference:	CS_WI_BS005
Effective Date:	02Dec2019		

even if they discontinue early.

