- “Presumed Persistence” if they are deemed a clinical failure, or if the clinical response is missing at the specific visit.
- Patients with missing clinical response are assigned a response of “No mycological or clinical follow-up available”.

For statistical analysis of mycological response, values will be assigned to the DRC-adjudicated and Investigator-assessed mycological response as follows:

- Success (Eradication, Presumed Eradication),
- Failure (Persistence, Presumed Persistence, Recurrent/Emergent infections, death or any other response except Eradication or Presumed Eradication).

Patients withdrawn from study medication due to an unsuccessful overall outcome are required per protocol to return

Document: \\weedc-vnasc01\BIOSdata\F2G\F901318 [Redacted]
 Author: [Redacted] Version Number: 3.0
 Version Date: 06Apr2023
 Template No.: CS_TP_BS016 Revision 6 Reference: CS_WI_BS005
 Effective Date: 02Dec2019

F2G Ltd.
PROTOCOL F901318/0032

for the main study phase EOT visit but will not be asked to return for the Day 42 and/or Day 84 visits; these patients will be considered as failures at all subsequent timepoints.

For the 4-week follow-up visit, only patients who did not enrol in the extension treatment phase will be considered.

16.1.5.6. All-cause mortality rate at Day 42, main study phase EOT, Day 84, and 4-week follow-up

All-cause mortality rate at Day 42, main study phase EOT, Day 84, and 4-week follow-up is a secondary efficacy variable.

Survival status is captured on the Survival Status eCRF page.

Mortality rate at visit X is calculated as:

$$\frac{\text{Number of deaths up to and including visit X}}{\text{mITT population}}$$

For the 4-week follow-up visit, only patients who did not enrol in the extension treatment phase will be considered.

16.1.5.7. Patient-reported outcome at Day 42 and Day 84

[figure not shown]
A secondary efficacy variable is the quality of life (patient-reported outcome) [redacted] based on the EQ-5D-5L questionnaire. Patient-reported outcome is collected on the Health Questionnaire eCRF page.

The EQ-5D-5L health questionnaire is an assessment where the following five qualitative items are evaluated, i.e. does the patient have issues with:

- Mobility
- Personal care
- Usual activities
- Pain/Discomfort
- Anxiety/Depression

Document: \\weedc-vnasc01\BIOSdata\F2G\F901318 [redacted]
Author: [redacted] Version Number: 3.0
Version Date: 06Apr2023
Template No.: CS_TP_BS016 Revision 6 Reference: CS_WI_BS005

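### The crude all-cause mortality rate counts any patient of unknown survival status as alive, so it is a lower bound and can understate mortality; no analysis counting unknowns as deaths is planned

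*SAP*

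**What the plan says.** The numerator of the mortality rate in SAP 16.1.5.6 is "Number of deaths up to and including visit X"; the denominator is the mITT population. Protocol 8.8.2 agrees: the rates are "based on all patients in the mITT population". The one stated restriction is at the 4-week follow-up, where the SAP considers only patients who did not enter extended treatment.

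SAP 16.1.6.2 gives the missing-data rule. Once a death is reported, "then the patient is considered as a death for subsequent visits". Where no death was reported earlier and "survival status is missing/not done at the specific visit", the status is labelled as missing and nothing further is done.

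SAP 16.1.7.5 adds three things. It seeks survival status by other routes (sponsor safety reviews and last known contact) where it was not collected at the visit. It puts a 95% exact Clopper-Pearson CI on the crude rate. It also plans Kaplan-Meier survival at Days 42, 84 and 112, censoring patients not known to have died at the last date they were known to be alive on the main study.

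For overall response the rule runs the other way. On the primary endpoint, "Patients with a missing DRC-adjudicated overall response at Day 42 will be considered as failures" (SAP 16.1.2). On the secondary overall response, "Patients with a missing overall response at a specific visit will be considered as failures at the visit" (SAP 16.1.6.1, which says the same for clinical response).

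**The concern.** A patient labelled as missing but kept in the denominator has the same effect on the rate as a confirmed survivor. The exact CI then treats that patient as an observed non-event, so it carries no uncertainty about the unknown outcome. The error can go in one direction only, towards lower mortality. For overall and clinical response, missing data instead count against the drug.

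Mortality is the endpoint least open to judgement in an open-label, single-arm trial. Protocol 8.1 speaks in general terms of comparing efficacy with external control data. If mortality enters such a comparison, a figure that can only err in the favourable direction is a weak basis for it. Loss may also be related to outcome. Patients withdrawn from drug or with an unsuccessful outcome are not asked back for Days 42 and 84, so their survival status has to be obtained in some other way.

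**Working it through.** Neither document states an expected mortality or an expected share of unknown status, so there is no planned figure to reproduce. The check is algebraic, followed by an illustration on assumed counts.

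**Inputs.** N = 200, the approximate planned enrolment in SAP 3.1, used as a stand-in for the mITT count. D = 40 known deaths (assumed). M = 0, 4, 10 or 20 patients of unknown status, that is 0%, 2%, 5% or 10% (assumed).

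**Formulas.**
- Planned crude rate: D/N.
- Known status only: D/(N − M).
- Unknown counted as death: (D + M)/N.

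The rate that full ascertainment would give lies between D/N and (D + M)/N. The planned rate is the lower end, and the possible shortfall runs from 0 to M/N. If unknown patients die at the same rate p as the others, then D = p(N − M) and the planned rate equals p(1 − M/N). A true 30% becomes 28.5% at 5% unknown and 27.0% at 10% unknown.

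**Results (N = 200, D = 40; exact 95% CIs).**

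| Unknown | Planned D/N | Known status only | Unknown as death |
|---|---|---|---|
| 0 | 40/200 = 20.0% (14.7-26.2) | 20.0% | 20.0% |
| 4 | 20.0% (14.7-26.2) | 40/196 = 20.4% | 44/200 = 22.0% (16.5-28.4) |
| 10 | 20.0% (14.7-26.2) | 40/190 = 21.1% | 50/200 = 25.0% (19.2-31.6) |
| 20 | 20.0% (14.7-26.2) | 40/180 = 22.2% | 60/200 = 30.0% (23.7-36.9) |

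The planned rate and its interval are the same in every row: they do not respond to the number unknown.

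**Small groups.** SAP 7.4 presents mortality by subgroup, including disease category. In a group of 20, one unknown patient moves the upper bound by 1/20 = 5 points.

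**Kaplan-Meier.** In 2,000 simulated trials of 200 patients with true Day 42 mortality of 30%, 10% of patients were subject to loss at times spread evenly over the 42 days and unrelated to death. The crude rate averaged about 28.6% and Kaplan-Meier 30.0%. Kaplan-Meier therefore removes the bias under non-informative loss. If those lost are at higher risk, it is also too low.

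**The case against.** The strongest reply is that the plan already limits the problem.

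- **Collection.** Protocol 6.3.2 requires survival status at Days 42 and 84 in all patients, whenever treatment stopped. The footnotes to Table 1, Section 5.1 and Section 6.3 apply this to withdrawn and unsuccessful patients, and Section 6.3 accepts phone contact. SAP 16.1.7.5 adds further sources. Nothing in the documents suggests that 5% or 10% will be unknown.
- **Kaplan-Meier.** The protocol synopsis names Kaplan-Meier as the method for mortality, and the SAP gives landmark rates that do not count unknowns as alive.
- **Display.** Unknown status is labelled as missing. If the count is tabulated, a reader can work out the upper bound.
- **Role.** Mortality is a secondary, descriptive endpoint with no hypothesis test.

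All of this stands, and it keeps the point small. It does not close it: the SAP still does not say how a remaining unknown should affect the crude rate, other than by adding to the denominator.

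A reader might infer that mortality is understated as a matter of fact. The documents do not support that: it requires that at least one patient of unknown status has died, and no missing rate is given. A reader might also infer that mortality reverses a uniform missing-equals-failure rule. There is no uniform rule. A patient without mycological follow-up is assigned presumed eradication, a success, if clinically successful (SAP 16.1.5.5), and missing radiology is shown as missing (SAP 16.1.6.1). The contrast holds for overall and clinical response only. Finally, a mortality comparison with historical rates is not specifically planned. The detailed comparisons concern response rates, and the mortality paragraph of Protocol 8.8.2 names none.

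**Conclusion.** The point holds in a limited form. As defined, the crude rate and its Clopper-Pearson CI give the lowest mortality compatible with the data, and they can understate it by up to M/N. On the assumed 200 patients and 40 known deaths, that is up to 2 points with 4 unknown, 5 with 10 and 10 with 20. If unknown patients resemble the rest, the like-for-like shift is much smaller: 20.0% to 21.1% with 10 unknown, against a CI about 11.5 points wide (26.2 − 14.7). With complete ascertainment it is zero.

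It would be tempting to conclude that making Kaplan-Meier the main estimate settles the matter. It does not, because outcome-related loss makes censoring informative and biases Kaplan-Meier in the same direction. A bound that assumes nothing about the unknowns is still needed, and none is planned. This is a cheap improvement to the plan, not a flaw that undermines the endpoint.

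**What to change.** In SAP 16.1.6.2 and 16.1.7.5, add at Days 42 and 84, overall and by disease category, a binomial mortality rate with exact 95% CI that counts unknown status as death. Show the number of patients of unknown status beside each crude rate, and present the new rate together with the Kaplan-Meier estimate already planned. The crude rate can stay as defined, read as the lower bound.

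The cost is one extra row per table and a slightly less favourable figure. No new data collection is needed.
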